3.8.3 Follow-Up Visits - Survival/Post-Disease Progression

Once a subject experiences confirmed disease progression or starts a new anti-cancer therapy, the subject moves into the survival follow-up phase and should be contacted (e.g., phone, email, etc.; in-person visit not required) at least every 3 to 6 months to collect information on new anti-cancer treatments received and to assess for survival status until death, withdrawal of consent, or the end of the study, whichever occurs first (see Study Calendar, Section 3.9). Any adverse events which

Abbreviated Title: RAdR for R/R TCM

Version Date: 12/04/2025

are present at the time of discontinuation should be followed in accordance with the safety requirements.

3.9 STUDY CALENDAR

Procedure	Screening	Baseline	Study Cycles					Disease Evaluations	End of Treatment and Disease Progression	Post-Treatment Follow-Up		
			C1			C2-6				Safety ¹	Follow-Up (Prior to PD)	Survival (Post-PD)
Scheduling Window (Days):	-35 to -8 ²		1 (±3)	10 (±3)	15 (±3)	1 (±3)	10 (±3)	Every 2 cycles ³	Treatment discontinuation/PD ⁴	Day 30 (+7)	Every 60 or 90 days ⁵	Every 3 months ⁶
Confirmation of Diagnosis ⁷	X											
Clonal T-cell receptor rearrangement by PCR	X											
Medical, social and disease history ⁸	X	X										
Physical Exam and ECOG PS ⁹	X	X	X			X			X	X	X	
Symptoms/Adverse Events Assessment, Concomitant Medication Review	X	X	X			X			X	X	X	
CBC with Differential	X	X	X	X		X	X		X	X	X	
Reticulocyte Count	X	X				X			X	X	X	
Chemistry Panels ¹⁰	X	X	X	X		X	X		X	X	X	
LDH, Serum Lipase and Amylase	X	X	X	X		X	X		X	X	X	
PT/INR and aPTT ²²	X	X				X			X	X	X	
TSH and free T4	X											
Urinalysis	X	X							X			
Pregnancy Test ¹¹	X	X	X (weekly during cycle 1)			X			X			
EKG, TTE	X											
Pulmonary function tests ¹²	X											

Procedure	Screening	Baseline	Study Cycles					Disease Evaluations	End of Treatment and Disease Progression	Post-Treatment Follow-Up		
			C1		C2-6					Safety ¹	Follow-Up (Prior to PD)	Survival (Post-PD)
Scheduling Window (Days):	-35 to -8 ²		1 (±3)	10 (±3)	15 (±3)	1 (±3)	10 (±3)	Every 2 cycles ³	Treatment discontinuation/PD ⁴	Day 30 (+7)	Every 60 or 90 days ⁵	Every 3 months ⁶
HBsAg, HBcAb, HCVAb, HIV Antibody, HTLV-1/2 ¹³	X											
Imaging studies ¹⁴	X	X						X	X		X	
MRI, Lumbar Puncture ¹⁵		X						X	X		X	
Bone Marrow Aspiration/Biopsy ¹⁶		X							X	X		
Flow Cytometry ¹⁷		X						X	X	X	X	
Clinical photography and dermatology assessment/ global score ¹⁸		X						X	X		X	
Radiologic Evaluation/ tumor measurement ¹⁹		X						X	X		X	
Uric Acid, Total Protein	X	X	X	X	X	X						
HLA typing (A, B, C, DR, DQ)	X											
T, B, NK cell subsets	X	X			X				X	X	X	
Iron panels, Folate, and B12, C-reactive Protein	X	X						X ²⁰				
Research Blood, Buccal and/or Saliva Samples ²¹	X		Refer to Table Section 5.1.1									
Tissue Samples	X											
Survival Status												X

NOTE: Any other tests should be performed as clinically indicated. See Section 3.4 for drug administration information. See Section 5 for information on research blood samples/correlative studies to be collected.

¹ 30 days (± 7) following last dose of any study drug (via clinic or phone). If initiating new anti-cancer therapy within 30 days after last dose of any study drug, 30-day safety follow-up visit must occur before first dose of new therapy.

² Screening and Baseline evaluations should be performed within 28 days prior to enrollment and dosing, respectively, unless otherwise noted and with the following exceptions: Confirmation of diagnosis (no time limit); HIV antibody, HTLV-1/2 serologies, Hepatitis B surface antigen and Hepatitis C antibody, EKG, TTE, bone marrow aspiration/biopsy and Clonal T-cell receptor rearrangement by PCR (all within 3 months), baseline pregnancy testing (within 10 – 14 days and within 24 hours prior to prescribing lenalidomide) **NOTE:** Any screening tests performed within the specified time frame for baseline do not need to be repeated.

³ To be performed on Day 21 (± 2 days) of Cycles 2, 4, and 6. Confirmatory scans should also be obtained 4 weeks following initial documentation of objective response.

⁴ To be done at end of treatment (30 days after last dose of study treatment; may be combined with 30 day safety follow-up, if timing coincides). If subject to initiate new anti-cancer therapy assessments should occur before the first dose of the new therapy.

⁵ Follow-up to occur about every 60 days (± 7 days) for first 6 months, every 90 days (± 14 days) for 2 years, then every 6 months (± 28 days) for another 2 years and then annually (± 6 weeks) until disease progression or initiation of new anti-cancer therapy.

⁶ After disease progression or initiation of new anti-cancer therapy, contact for survival about every 3 to 6 months (± 4 weeks).

⁷ Pathologic review/confirmation of diagnosis by Laboratory of Pathology, NCI (no time limit). If archival sample is not available or not adequate, a fresh tumor biopsy and/or peripheral blood sample will be obtained.

⁸ Complete medical history at screening/baseline. Interim on study and in follow-up. Disease and social history required only at screening.

⁹ Physical exams to include vitals, weight, and height (screening only).

¹⁰ Chemistry panels include: Acute care, Hepatic, and Mineral. For screening, Chemistry panels (as noted) or specific analyte required for eligibility, including: Creatinine (i.e., Acute Care Panel); serum calcium, phosphate, magnesium and albumin (i.e., Mineral Panel); ALT, AST, total bilirubin (i.e., Hepatic Panel, direct bili if indicated). If a patient has physical exam evidence or complains of symptoms suggestive of rhabdomyolysis, clinical work-up will be performed (e.g., creatinine kinase, aldolase, possibly serum myoglobin and additional urine studies) to determine if the patient is experiencing rhabdomyolysis and the tests will be repeated to monitor for resolution of this event; dose modification or interruption or discontinuation of treatment will occur, as needed.

¹¹ Individuals of childbearing potential with regular or no menstrual cycles must agree to have pregnancy tests weekly for the first 28 days of lenalidomide treatment, including dose interruptions and then every 28 days throughout the remaining duration of lenalidomide treatment, including dose interruptions, at lenalidomide discontinuation, and at Day 28 following lenalidomide discontinuation. If menstrual cycles are irregular, the pregnancy testing must occur weekly for the first 28 days of lenalidomide treatment, including dose interruptions, and then every 14 days throughout the remaining duration of lenalidomide treatment, including dose interruptions, at lenalidomide discontinuation, and at Day 14 and Day 28 following lenalidomide discontinuation.

¹² Diffusing capacity/alveolar volume (DLCO/VA) forced expiratory volume in 1 second (FEV1) for patients with significant pulmonary or smoking history.

¹³ HBV DNA PCR, HCV PCR, and/or HIV 1/2 viral load will be tested for patients with positive serologies.

¹⁴ At screening CT scans of neck, chest, abdomen, and pelvis should be performed (with IV and PO contrast, unless patient is allergic or has renal insufficiency; other imaging may be substituted at the discretion of the investigator). Other body areas may be imaged if clinically indicated. MRI of the brain is only required

in patients with suspected involvement of CNS. Also, at screening, a FDG-PET/CT torso (extremities to be included if there is confirmed or suspected disease involvement). At baseline one or more of the following studies: CT, MRI, FDG-PET/ CT and or clinical photography; MRI of the brain is only required in patients with suspected involvement of CNS. A FDG-PET/ CT will be done after Cycle 2 and at the End of Treatment.

¹⁵ Patients with neurological symptoms or signs should undergo MRI scan of the brain and lumbar puncture.

¹⁶ Baseline bone marrow aspiration/ biopsy with flow cytometry must be done within 3 months prior to starting treatment. During post-treatment follow-up, repeat bone marrow aspiration/ biopsy needed only to confirm a CR.

¹⁷ Clinical peripheral blood flow cytometry (Laboratory of Pathology, NCI) may be done for disease evaluation of patients who had circulating leukemic cells detected at baseline, and for patients with CTCL regardless of their baseline results.

¹⁸ To be performed in selected patients with cutaneous disease (as determined by PI or AI).

¹⁹ Dermatology assessment & Global/mSWAT scoring be used instead of/ in addition to radiologic evaluation for patients with predominantly cutaneous disease.

²⁰ Patients with elevated CRP and soluble IL2Ra will have them repeated every 6 weeks as part of disease evaluation.

²¹ Samples for correlative research are to be collected as indicated in Section 5. If archival tissue is not available or adequate, baseline punch biopsy of the skin or core needle biopsy of a lymph node/visceral lesion is required, otherwise this is optional.

²² PT/ INR and aPTT are required at screening, baseline and before procedures (as clinically indicated). Other timepoints are optional as tubes are available.

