3.2.1 Hematologic exceptions

- Grade 3 or 4 lymphocytopenia without clinical signs of infection grade 2 or above.
 - Lenalidomide, romidepsin and CC-486 (5-azacitidine) will be continued in the event of asymptomatic grade 3 or 4 lymphocytopenia, unless there are clinical signs of significant infection (persistent fevers, labile blood pressure, localized complaints or findings on physical examination, hypoxia or organ dysfunction).
- Grade 3 neutropenia without clinical signs of infection grade 2 or above.
 - Lenalidomide, romidepsin and CC-486 (5-azacitidine) will be continued in the event of grade 3 neutropenia unless there are clinical signs of significant infection, as listed above.
- Grade 3 thrombocytopenia without signs of bleeding that resolved within 7 days of holding the study drug(s) (See Section 3.5.1 for study drug holding parameters).
- Grade 3 anemia that improves to Grade ≤ 2 after transfusion of up to two units of pRBCs and does not recur within 7 days.
- Grade 3 febrile neutropenia (grade 3 febrile neutropenia at any time during therapy will be considered an SAE but not DLT)

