3.5.1 Treatment modifications for adverse reactions

All treatment modifications should be discussed with the senior clinical investigators on the study. Treatment modifications will follow the guidelines outlined in [Table 6](#). Any given dose modification after Cycle 1 can be repeated twice in a patient as long as the patient is benefiting from therapy and does not meet off-treatment criteria.

If a toxicity which requires modification of therapy per [Table 6](#) occurs during the window period (day -7 to day -1) and does not meet the definition of a DLT, cycle 1 day 1 may start after resolution to grade ≤ 1 (grade ≤ 2 for anemia).

All grading scales in the following tables are according to the revised NCI Common Terminology Criteria for Adverse Events (CTCAE) version 5.0.

Table 6: Dose Modification of Lenalidomide, romidepsin and CC-486 (5-azacitidine) for treatment related AEs

Event	Initial management	Follow-up Management
Cycle 1 DLT Evaluation Period		
Grade 1 AEs		
Any AE	Continue treatment	Continue monitoring and laboratories at least once weekly
Grade 2 AEs		
ANC: $<1.5 - 1.0 \times 10^9/L$	Continue treatment	Monitor cell counts at least twice weekly Pegfilgrastim*

Event	Initial management	Follow-up Management
Platelet: < 75,000 - 50,000/mcL	Consider holding treatment for up to 7 days	Monitor cell counts at least twice weekly Restart treatment when platelet count >75,000/mcL
Hgb: < 10.0 - 8.0g/dL	Continue treatment	Monitor cell counts at least twice weekly Consider transfusion before cycle 2
Any other AE	Continue treatment	Continue monitoring and laboratories once weekly
Grade 3 AEs		
ANC: <1.0 -0.5 x 10⁹/L	Hold treatment for up to 7 days Restart treatment at full doses	Monitor cell counts at least twice weekly G-CSF# and Pegfilgrastim*;
Platelet: <50,000 - 25,000/mcL	Hold treatment for up to 7 days Restart treatment at when platelets > 75,000/mcL	Monitor cell counts at least twice weekly If platelets are not > 75,000/mcL the patient is off treatment DLT
Hgb < 8.0g/dL	Hold treatment for up to 7 days Restart treatment after transfusion	Monitor cell counts at least twice weekly Transfusion until Hgb > 9 g/L
Any other AE	Hold treatment for up to 7 days Restart treatment when AE has resolved to ≤ grade 1	Continue monitoring and laboratories at least twice weekly If the AE has not improved to ≤ grade 1, the patient is off treatment DLT
Grade 4 AEs at any time during cycle 1		
Any AE	Discontinue treatment	Off treatment DLT
Cycles 2 through 6		

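### No blood count is scheduled between day 10 and the next cycle, and AE review is scheduled only on day 1, so a silent late cytopenia in cycle 1 of Arm 3 can go unseen

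*Combined protocol and SAP*

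**What the plan says.** **Study calendar, Section 3.9.**
- The rows "CBC with Differential" and chemistry panels are marked on days 1 and 10 of cycle 1 and of cycles 2-6. Both are blank at cycle 1 day 15.
- The row "Symptoms/Adverse Events Assessment, Concomitant Medication Review" is marked on day 1 of each cycle. It is blank on day 10 and at cycle 1 day 15.
- The row "Uric Acid, Total Protein" is marked at cycle 1 day 15, so blood is already due at that timepoint.
- The disease evaluation column, "To be performed on Day 21 (± 2 days) of Cycles 2, 4, and 6", carries no count and no AE mark.
- The note under the table adds only this: "Any other tests should be performed as clinically indicated".

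**Table 6, Section 3.5.1.** For any grade 1 AE, in cycle 1 and again in cycles 2-6, the follow-up is "Continue monitoring and laboratories at least once weekly". For grade 2 and 3 cytopenias in cycle 1 it is "Monitor cell counts at least twice weekly". Any grade 4 AE in cycle 1 ends treatment and is a DLT.

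**DLT window, Section 3.2.** The window runs to the end of cycle 1. The text still gives day 22 as the usual end, from the former 21-day cycle; Section 3.4.2 sets the current cycle at 28 days.

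**The concern.** The toxicity rules assume that somebody is looking at the counts after day 10, but the calendar does not schedule anyone to look. Table 6 steps up monitoring once an AE is known. A cytopenia that starts silently after day 10 cannot set off monitoring that depends on its own detection. If the patient had no earlier AE, the next routine count is the one before cycle 2.

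That count favours recovered patients. Section 3.4.2 holds the next cycle until the entry laboratory limits are met, so a prolonged cytopenia shows up as a delay, while one that has come and gone leaves no trace.

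Arm 3 is the only arm enrolling. It runs on a schedule adopted after escalation: 28-day cycles without the lenalidomide lead-in. Cytopenias are a main expected toxicity. Table 5 gives grade 3-4 platelet decreases in 12 of 25 patients (48%) and neutrophil decreases in 10 of 25 (40%) for romidepsin with 5-azacitidine. The stake is an understated rate of grade 3-4 haematologic toxicity in Arm 3, incomplete laboratory shift tables by time (Section 10.4.2), and late management of events that Table 6 would act on.

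**Working it through.** **1. The plan's own figure.** The plan gives no figure for missed toxicity. Its one figure that depends on seeing every DLT is the escalation table in Section 10.2. The formula (1-p)^3 + 3p(1-p)^5 at p = 0.1 to 0.6 gives 0.906, 0.709, 0.494, 0.309, 0.172 and 0.082, which round to the plan's 0.91, 0.71, 0.49, 0.31, 0.17 and 0.08. That table is correct and is not in dispute.

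**2. Length of the gap.** Inputs: counts on days 1 and 10, each ±3 days; cycle length 28 days.
- Interval between counts: 29 - 10 = 19 days, so days 11-28 (18 days) have none.
- With the windows: shortest (29 - 3) - (10 + 3) = 13 days, longest (29 + 3) - (10 - 3) = 25 days.
- Former 21-day cycle: 22 - 10 = 12 days, so days 11-21 (11 days) had none.
- AE assessment: 28 days apart, 22 to 34 with the windows.
- Table 6 once triggered: at most 7 days between laboratories.

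Whether the DLT window ends on day 22 or day 28, no routine count falls in it after day 10.

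**3. Illustration: a patient with no earlier trigger.** Assumptions, none of them from the documents: the episode starts on any of days 11-28 with equal chance, lasts a fixed 5 or 7 days, and is seen only if a count falls inside it.

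| Counts on days | 7-day episodes missed (start days) | 5-day episodes missed (start days) |
|---|---|---|
| 10, 29 | 12/18 = 67% (11-22) | 14/18 = 78% (11-24) |
| 10, 15, 29 | 7/18 = 39% (16-22) | 9/18 = 50% (16-24) |
| 10, 15, 22, 29 | 0/18 = 0% | 4/18 = 22% (16, 17, 23, 24) |

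**4. From such patients to all patients.** Let u be the share of late episodes that arise in patients with no earlier trigger. The documents do not give u. Suppose that everyone else has weekly laboratories, as in the last row.
- Seven-day episodes missed = u × 12/18: 0% at u = 0, 33% at u = 0.5, 67% at u = 1.
- Five-day episodes missed = u × 14/18 + (1 - u) × 4/18: 22%, 50% and 78% at the same values.

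Table 5 suggests that u is well below 1: platelet decreases of any grade in 72%, neutrophil decreases in 68%, nausea in 68%, fatigue in 56%. It does not say in which cycle or on which day they began, so it does not fix u.

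**5. Robustness of the table reading.** In the second half of the calendar, HLA typing stands under screening, while Section 2.6.2 lists it at baseline, so that half may have slipped one column in the PDF reading. The uric acid and total protein row has six consecutive marks, from screening to day 1 of cycles 2-6. Moved one column to the right, it still covers cycle 1 day 15. The count and AE rows are in the first half and show no such slip.

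**The case against.** The strongest reply is that the calendar is not the only operative text. Table 6 makes laboratories weekly after any grade 1 AE and counts twice weekly after a grade 2-3 cytopenia in cycle 1. Most patients on this combination will probably have some AE by day 10. Section 6.1.1 records AEs continuously until 30 days after the last intervention, Section 3.7 requires pre-dose assessments on day 10, the team discusses each patient at least weekly (Section 7.4.1), and the diary asks patients to report side effects. All of this stands, and it confines the point to asymptomatic cytopenias in patients with no earlier trigger.

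It also rules out several stronger readings that a reader might draw:
- *The DLT exceptions that turn on recovery within 7 days cannot be assessed.* They can for a detected event, because Table 6 then requires serial counts.
- *67% or 78% of late cytopenias will be missed.* Those figures hold only at u = 1 and under the assumed onset and duration. The documents do not say when counts reach their lowest point.
- *The primary endpoint is biased.* Section 10.1 lists the MTD and the frequency of treatment-emergent AEs, not a DLT rate. Under Section 6.1.2.1 a silent, untreated laboratory change may not be an AE even if sampled.
- *The 20 mg MTD is too high.* Escalation is closed, and the calendar used during it is not shown, so nothing can be inferred either way.
- *A day 22 draw is already required for everyone.* Table 6's weekly laboratories are conditional follow-up.

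What none of the safeguards does is detect a symptomless fall in counts that begins after day 10 with no prior AE.

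**Conclusion.** The point holds in a limited form. The calendar leaves 18 days of each 28-day cycle without a scheduled count and marks AE assessment only every 28 days, and Table 6 closes the gap only for patients already known to have an AE. A silent cytopenia in the remaining patients can pass unseen within the cycle 1 DLT window, so grade 3-4 haematologic toxicity in Arm 3 can be understated and its management delayed.

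The size cannot be fixed from the documents. Under the assumptions above it ranges from 0% to 67% of seven-day episodes and from 22% to 78% of five-day episodes, depending on how many arise without an earlier trigger. The conclusion rests on the blank cells being blank in the source table. It does not extend to the declared MTD or to symptomatic AEs.

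**What to change.** 1. Check the blank cells in Section 3.9 against the source table.
2. Mark blood count with differential and chemistry at the existing cycle 1 day 15 timepoint.
3. Mark AE assessment at day 10 of every cycle and at cycle 1 day 15.
4. Reconcile the rest of the interval with Table 6. With day 15 marked, days 16-28 of cycle 1 (13 days) still have no scheduled count. In cycles 2-6 the 18-day gap remains. Section 3.9 should state whether the weekly laboratories in Table 6 apply to every patient or only after an AE. That choice is the sponsor's.

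Cost: a calendar edit, one added routine test at a draw that already takes place, and short AE reviews at existing visits. If item 4 leads to further counts, Section 3.7 lets the investigator accept results from outside NIH.

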3.10 COST AND COMPENSATION

3.10.1 Costs

NIH does not bill health insurance companies or participants for any research or related clinical care that participants receive at the NIH Clinical Center. If some tests and procedures are performed outside the NIH Clinical Center, participants may have to pay for these costs if they are not covered by insurance their company.

3.10.2 Compensation

No direct compensation will be provided on the study.

3.10.3 Reimbursement

The NCI will cover the costs of some expenses associated with protocol participation. Some of these costs may be paid directly by the NIH and some may be reimbursed to the subject as appropriate. The amount and form of these payments are determined by the NCI Travel and Lodging Reimbursement Policy.

3.11 CRITERIA FOR REMOVAL FROM PROTOCOL THERAPY AND OFF STUDY CRITERIA

Prior to removal from study, effort must be made to have all patients complete a safety visit approximately 30 days following the last dose of study therapy. Additional safety visits and follow-up will continue as per Section [3.8](#).

3.11.1 Criteria for removal from protocol therapy

Patients who meet the following criteria should be discontinued from protocol therapy:

- Completion of protocol therapy (i.e., up to 6 cycles)
- Confirmed disease progression
- Intercurrent illness that prevents further administration of treatment
- Unacceptable toxicities as listed in Section [3.9](#) or those toxicities listed in Section [3.5](#) that requires treatment to be stopped.
- Subject's request to withdraw from protocol therapy
- Investigator's decision to withdraw the patient
- Subject's non-compliance with trial treatment or procedure requirements that requires removal in the opinion of the PI
- Pregnancy
- The drug manufacturer can no longer provide the study agent
- Study is cancelled for any reason

3.11.2 Off-Study Criteria

- Subject requests to be withdrawn from study
- Subject is lost to follow-up
- Death
- Study is cancelled for any reason

3.11.3 Lost to Follow-up

A participant will be considered lost to follow-up if they fail to return for two (2) scheduled visits and is unable to be contacted by the study site staff.

The following actions must be taken if a participant fails to return to the clinic for a required study visit:

- The site will attempt to contact the participant and reschedule the missed visit within 3 business days and counsel the participant on the importance of maintaining the assigned visit schedule and ascertain if the participant wishes to and/or should continue in the study.
- Before a participant is deemed lost to follow-up, the investigator or designee will make every effort to regain contact with the participant (where possible, 3 telephone calls and, if necessary, an IRB approved certified letter to the participant's last known mailing address or local equivalent methods). These contact attempts should be documented in the participant's medical record or study file.
- Should the participant continue to be unreachable, they will be considered to have withdrawn from the study with a primary reason of lost to follow-up.

